**The Drain Debate: Reevaluating Prophylactic Drains in Total Gastrectomy- A
Controlled Trial on the Use of Prophylactic Drains in Total Gastrectomy for
Gastric Cancer (DRAG Study)**

Trial registration: Clinical Trials.gov NCT 04288661

Upload date: 01/02/2021

STUDY PROTOCOL

The DRAG (DRains After Gastrectomy) Trial is a prospective, non-randomized, controlled clinical trial involving patients diagnosed with gastric neoplasm. All surgeries were performed by a single, highly experienced surgeon in the 1st Propaedeutic Surgery Department at Hippocration General Hospital in Athens, Greece. The patients underwent open total gastrectomy with D2 lymph node dissection, followed by Roux-en-Y gastrointestinal tract reconstruction, in accordance with a predefined, ERAS-compliant perioperative departmental protocol. Our institution's protocol does not routinely incorporate exploratory laparoscopy or peritoneal cytology.

The participants were divided into two groups. The first group followed the department's standard practice, with a drain placed near the esophagojejunal anastomosis (drain group). In contrast, the second did not have a drain placed (non-drain group). The decision to place a drain was based on the following criteria:

- a) Pulmonary diseases under oxygen therapy
- b) Chronic oral steroid use (≥ 5 mg/day prednisone equivalent for > 1 month)
- c) Intraoperative hemodynamic instability requiring vasopressors
- d) Intraoperative blood loss exceeding 250 mL
- e) Vessel injury (celiac axis or its branches)
- f) Injury to adjacent structures (pancreas, spleen, duodenum)
- g) Tension of the anastomosis
- h) Uncertainty regarding duodenal stump integrity due to either staple misfire or tissue quality issues

Per our departmental protocol, patients were gradually mobilized starting directly after surgery, when feasible. On the second postoperative day, an oral gastrografin study was conducted for each patient to detect any early anastomotic leaks. Following a normal radiological study, patients were initiated on a liquid diet, which was then advanced to pureed food on the third postoperative day, and a soft diet on the fourth day. For patients in the drain group, the drain was removed on the fifth postoperative day, provided that the drainage volume was less than 50 mL over the preceding 48 hours, in line with departmental protocol. A descriptive timeline of the protocol is presented in the the table below.

a) Appendix 1. Timeline of study protocol

STUDY PERIOD									
	ENROLLMENT DAYS		DAY OF SURGERY	POSTOPERATIVE DAYS					
TIMEPOINT	-7 TO -2	-1	0	1	2	3	4	5	Ω
ENROLLMENT									
PATIENT SELECTION	X								
PREOP CHECK	X								
CONSENT SIGN		X							
PROTOCOL EDUCATION		X							
INTERVENTION									
DRAIN PLACEMENT			X						
INTRAOPERATIVE DATA RECORDING			X						
MONITORING									
CLIN. EXAMINATION & VITALS				X	X	X	X	X	X
LABS				X	X	X	X	X	X
DRAIN CONTENT MONITORING			X	X	X	X	X	X	X
ORAL CONTRAST STUDY					X				
PONV				X	X	X	X	X	
PAIN (VAS SCORE)			X	X	X	X	X	X	
SSI				X	X	X	X	X	
MOBILIZATION				X	X	X	X	X	
ORAL FEEDING				X	X	X	X	X	
GUT MOTILITY				X	X	X	X	X	X
EXTRAABDOMINAL COMPLICATIONS				X	X	X	X	X	
LOS				X	X	X	X	X	X
MORTALITY				X	X	X	X	X	X
READMISSIONS				X	X	X	X	X	X
REOPERATIONS									

b) LOS: length of stay, SSI: surgical site infection, VAS score: visual analogue score

c) Ω: time between POD#5 and discharge

This study was conducted in accordance with the principles outlined in the Helsinki Declaration of Human Rights and with the Guidelines of Good Clinical Practice. The final study protocol and the informed consent form for participant inclusion received approval from the Institutional Review Board (IRB). The IRB also conducted regular assessments, as required, to ensure the ongoing compliance with lawful medical practice throughout the trial.

The statistical analysis was performed using the R software (R foundation for Statistical Computing) version 4.3.0 for Windows. Descriptive characteristics for the quantitative data were expressed as median and Quartile 1 (Q1) to Quartile 3 (Q3) range and for completeness reasons the mean \pm standard deviation (SD), for the qualitative data was reported the frequency of occurrence and the relevant percentage. Comparisons were preformed between patients with drainage and those without drainage; for the qualitative parameters statistical tests were performed via the chi-square test (and if required a Fisher exact test) and for the arithmetic data (as normality was not possible to be ensured using the Shapiro Wilk test), were applied not parametric tests, specifically the Mann Whitney U test. The significance level (p-value) was set to 0.05, thus statistically significant difference between compared groups was for $p < 0.05$ and all tests were two sided.

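### Drains were placed according to risk criteria a) to h), yet drained and undrained patients are compared without adjustment, so the comparison is open to confounding by indication

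*Combined protocol and SAP*

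**What the plan says.** The design statement in the Study Protocol text reads: "The DRAG (DRains After Gastrectomy) Trial is a prospective, non-randomized, controlled clinical trial involving patients diagnosed with gastric neoplasm". The title announces the aim as "Reevaluating Prophylactic Drains in Total Gastrectomy".

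Two sentences describe who received a drain:

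- Group definition: "The first group followed the department's standard practice, with a drain placed near the esophagojejunal anastomosis (drain group". The second group had no drain.
- Assignment: "The decision to place a drain was based on the following criteria". The list a) to h) follows. Items a) and b) are preoperative (lung disease on oxygen, long-term steroids). Items c) to h) arise in theatre: "Intraoperative hemodynamic instability requiring vasopressors", blood loss above 250 mL, vessel injury, injury to neighbouring organs, a tense anastomosis and a doubtful duodenal stump.

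The statistical analysis paragraph after Appendix 1 says: "Comparisons were preformed between patients with drainage and those without drainage". It names chi-square (Fisher where required) for qualitative data and Mann-Whitney U for numerical data, two-sided at 0.05. It mentions no regression, stratification, matching, weighting, restriction or sensitivity analysis.

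**The concern.** The stated reason for draining a patient is a list of things that plausibly predict a worse course, and the analysis ignores that list. If the criteria raise the risk of complications, the crude tests will tend to make drains look harmful, and leaving them out look safe, even if drains do nothing. A real benefit could be hidden in the same way. This direction applies to complication-type outcomes. For pain, nausea or gut motility, the documents give no basis for a direction.

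Six of the eight criteria become known only during surgery. A well-balanced preoperative baseline table would therefore not exclude the problem, and adjustment for preoperative factors alone would not remove it.

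Drained against undrained is the only comparison described, so the weakness reaches every comparative result.

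**Working it through.** **Step 1: what is controlled.**

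| Source of difference between groups | Handling in the documents |
|---|---|
| Surgeon | Constant: "All surgeries were performed by a single, highly experienced surgeon" |
| Operation | Constant: open total gastrectomy, D2 dissection, Roux-en-Y |
| Perioperative care | Constant: "in accordance with a predefined, ERAS-compliant perioperative departmental protocol" |
| Criteria a) to h) | Given as the basis for drain placement; not restricted, stratified or adjusted for |

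**Step 2: is there a figure to reproduce?** No. The documents give no sample size, event rate, effect size or adherence to the criteria. Only the two-sided 0.05 level is stated. Everything below is illustration on assumed inputs.

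**Step 3: crude risks when the drain has no effect.** Let p0 be the risk without any criterion, RR the risk ratio for having one, and q the share of a group that has one.

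Crude risk = q × p0 × RR + (1 − q) × p0

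Assume p0 = 20% and RR = 2. For partial adherence, assume 40% of patients meet a criterion.

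- *Full adherence* (q = 1 drained, q = 0 undrained): 40% vs 20%, crude RR 2.00.
- *90% of criterion-positive and 10% of criterion-free patients drained*: share drained = 0.4 × 0.9 + 0.6 × 0.1 = 0.42; q = 0.36/0.42 = 0.857 drained and 0.04/0.58 = 0.069 undrained; risks 37.1% vs 21.4%, crude RR 1.74.
- *80% and 40% drained*: share drained = 0.32 + 0.24 = 0.56; q = 0.32/0.56 = 0.571 and 0.08/0.44 = 0.182; risks 31.4% vs 23.6%, crude RR 1.33.
- *Criteria equally common in both groups*: crude RR 1.00, so no bias from this source.

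**Step 4: chance of a significant drain-worse result.** Exact binomial enumeration, with Fisher when any expected count is below 5 and chi-square otherwise. Ranges are with and without continuity correction, since the plan does not say which applies. Group sizes are drained vs undrained and are assumed.

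| Scenario | About 80 patients | About 150 patients |
|---|---|---|
| Full adherence, 40% vs 20%, equal groups | 41% to 50% (40 vs 40) | 71% to 77% (75 vs 75) |
| Same, smaller drain group | 35% to 40% (20 vs 60); 25% (10 vs 70) | 61% to 68% (38 vs 112); 42% to 44% (19 vs 131) |
| 90%/10% drained | 26% to 34% (34 vs 46) | 49% to 57% (63 vs 87) |
| 80%/40% drained | 8% to 11% (45 vs 35) | 14% to 18% (84 vs 66) |
| Weaker criteria, RR 1.5, full adherence | 12% to 18% (40 vs 40); 10% (10 vs 70) | not run |
| Lower base risk, 10% vs 5%, full adherence | 4% to 5% (40 vs 40); 11% (20 vs 60) | 13% to 20% (75 vs 75) |
| No confounding, 20% vs 20% | 1% to 3% | 1% to 3% |

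A larger sample makes a false finding more likely, not less.

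**Step 5: if drains truly halved the risk** (20% base risk, criterion RR 2). Halving the drained risks of Step 3 gives 20.0% vs 20.0% (crude RR 1.00) with full adherence, 18.6% vs 21.4% (0.87) at 90%/10%, and 15.7% vs 23.6% (0.66) at 80%/40%. The true value is 0.50 in each case.

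**Step 6: can adjustment rescue it?** Only with overlap. Under full adherence no drained and undrained patients share the same criterion status, so no regression can separate the drain from its indication.

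**The case against.** Four points deserve weight.

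- *The mechanism rests on an ambiguous passage.* Drains are called standard practice for one group and also criteria-based. The criteria may have assigned everyone, kept some patients out of the no-drain group, or explain only some of the drains. If they were equally common in both groups, this bias disappears. This stands, and it is why the conclusion is conditional. It does not clear the plan, because no other rule for dividing the participants is given.
- *The rejection probabilities depend heavily on base risk.* This also stands. At 5% vs 10% they fall to 4% to 5% at 40 vs 40, so rare outcomes such as death would seldom give a false significant result in samples of that size. The crude risk ratio is still 2, so the estimate is as biased as before.
- *One surgeon, one operation and one care pathway.* These remove real sources of variation but do not balance a) to h).
- *The text is in the past tense, declares the lack of randomization, and states no causal hypothesis.* That is fair, and it makes the remedy largely one of analysis and reporting. However, a controlled trial that sets out to reevaluate drains and reports p-values between groups invites a causal reading.

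**Conclusion.** The concern holds. On the documents' own wording, exposure was decided by risk markers that the analysis does not handle, so the drained versus undrained comparison is confounded by indication to the extent that the criteria drove drain use. That the plan leaves this unaddressed is certain. How large the bias is cannot be settled from the documents. Across the assumed scenarios with a doubling of risk, the crude risk ratio under no drain effect runs from 1.33 to 2.00, and it would be 1.00 if the criteria were balanced. The direction against drains assumes that the criteria raise complication risk. This must be fixed before any between-group difference is read as evidence about drains.

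**What to change.** 1. Reconcile the standard-practice sentence with the criteria sentence, stating how each patient came to be in a group. Tabulate criteria a) to h) by drain group as far as the recorded data allow.
2. If criterion status is available and criterion-free patients occur in both groups, base the between-group comparison on them. Report an estimate with 95% CI: a risk difference for binary outcomes, and a difference in medians or Hodges-Lehmann shift for numerical ones such as length of stay or pain score. Adjust for recorded preoperative factors only where numbers permit. Label the analysis post hoc if it is chosen after the data are seen. State that residual confounding remains possible, because the reason for draining a criterion-free patient is not documented. Report criterion-positive patients descriptively.
3. If there is no overlap, or criterion status was not recorded for undrained patients, present the tests as descriptive and make no claim about the effect of drains. Where the records show that undrained patients were criterion-free, limit the conclusion to outcomes of omitting a drain in such patients.

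**Cost.** One table and revised wording, with no new patients or procedures, provided criterion status was recorded for everyone. Check this first: the Appendix 1 rows for the preoperative check and intraoperative data do not define their contents. If it was not recorded, only the wording change in step 3 is possible.

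The price is precision, and possibly the comparative claim itself. Of 80 patients in the assumed scenarios, 48 are criterion-free: about 19 drained vs 29 undrained at 80%/40%, or 5 vs 43 at 90%/10%. At 20% risk the 95% half-width, 1.96 × √(0.16/n1 + 0.16/n0), is about 23 and 37 percentage points respectively; the second is rough with only 5 patients.

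### Does observing drain content in one group only bias the comparison of leaks or other intra-abdominal events?

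*Combined protocol and SAP*

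**What the plan says.** The Study Protocol section describes two groups, one with a drain close to the esophagojejunal anastomosis and one without. Both had the same leak test: "On the second postoperative day, an oral gastrografin study was conducted for each patient to detect any early anastomotic leaks". Feeding followed it: "Following a normal radiological study, patients were initiated on a liquid diet". The one stated use of drain output is the removal rule: "the drain was removed on the fifth postoperative day, provided that the drainage volume was less than 50 mL over the preceding 48 hours".

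Appendix 1 has a row for "DRAIN CONTENT MONITORING" and rows for "CLIN. EXAMINATION & VITALS" and for laboratory tests. It also has a row for "EXTRAABDOMINAL COMPLICATIONS", but none for leak, collection, fistula or any other intra-abdominal event. Surgical site infection has a row, but the footnote only spells out the abbreviation ("SSI: surgical site infection").

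The statistical analysis paragraph compares patients with and without drainage, using chi-square or Fisher tests for qualitative data. It names no outcome.

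**The concern.** The exposure under study is also a possible way of seeing an outcome. Drain fluid can be inspected in one group and not in the other, beside the anastomosis where a leak would arise. The only leak-specific test common to both groups is done once, before oral feeding starts. Later leaks would have to be found by other routes, and a drain might reveal some that would otherwise go unnoticed.

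With no common event definition, the same true leak could then be counted in a drained patient and missed in an undrained one. At equal true risk the drain group would appear to have more events, and the comparison would favour omitting the drain. This would be separate from the confounding created by placing drains according to criteria a to h.

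**Working it through.** The documents give no sample size, event rate or detection rate, so there is no planned figure to reproduce. The check has three parts.

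**1. What each group is observed for (marks in Appendix 1; Ω is the time from POD5 to discharge)**

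| Row | Marks | Total | After POD2 | Available to |
|---|---|---|---|---|
| Drain content | day 0, POD1–5, Ω | 7 | 4 | drain group only |
| Oral contrast study | POD2 | 1 | 0 | everyone |
| Examination and vitals | POD1–5, Ω | 6 | 4 | everyone |
| Laboratory tests | POD1–5, Ω | 6 | 4 | everyone |

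After POD2 the shared rows carry the same four marks as drain content: POD3, 4, 5 and Ω. The Ω mark for drain content applies only while a drain is still in place, and the removal rule takes many or all drains out on POD5. Setting seven drain marks against one contrast study is therefore not like for like. The documents give drain content no assay, appearance rule or diagnostic threshold. Of the tests they describe as leak tests, one is shared and none belongs to the drain group alone.

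**2. How large the distortion could be (all inputs assumed)**

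Let p be the true risk, equal in both groups, and m the share of true events never recorded without a drain. As an upper limit, suppose the drain reveals all of these. Recorded risk is p with a drain and p(1 − m) without, so the ratio is 1/(1 − m) and the difference is p × m. With p = 10%:

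| m | Ratio 1/(1 − m) | Difference p × m |
|---|---|---|
| 0% | 1.00 | 0 points |
| 5% | 1.05 | 0.5 points |
| 10% | 1.11 | 1.0 point |
| 20% | 1.25 | 2.0 points |

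A different choice of inputs gives a different answer. Take 95% detection with a drain and p = 10%.

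- 80% detection without a drain: 9.5% against 8.0%, ratio 0.95/0.80 = 1.19.
- 60% detection without a drain: 9.5% against 6.0%, ratio 0.95/0.60 = 1.58.

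The chance that a two-sided 5% test rejects is Φ((d − 1.96·se₀)/se₁) + Φ((−d − 1.96·se₀)/se₁). Here d is the difference in recorded risk, p₁ and p₂ are the recorded risks and p̄ is their mean. With n per group, se₀ = √(2p̄(1 − p̄)/n) and se₁ = √((p₁(1 − p₁) + p₂(1 − p₂))/n).

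- 80% detection: about 6%, 7% and 8% for n = 50, 100 and 200.
- 60% detection: about 10%, 15% and 26%.

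The result is set by the assumed detection rate, about which the documents say nothing.

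**3. Whether dropping drain-detected events would help**

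Let e be the share of drain-group events that shared routes would have found but that the drain revealed first. Removing every event found through the drain leaves p(1 − m)(1 − e) against p(1 − m), a ratio of 1 − e: 1.00, 0.95, 0.90 and 0.80 for e = 0, 5, 10 and 20%. With m = e = 10%, the two counts give 0.90 and 1.11, on either side of the true value of 1.

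That bracket holds only if shared routes detect equally well in both groups and the drain does not alter whether an event occurs. Let T be the true ratio and k the ratio of shared-route detection, drain to no drain. The reduced count then gives T × k × (1 − e). At e = 10%, any k above 1/0.9 = 1.11 pushes it above T, and it is no longer a lower limit. Drains were placed for anastomotic tension, doubtful stump integrity and organ or vessel injury, so closer watching of drained patients is plausible. Whether a drain changes outcome is the study's own question.

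**The case for a change.** The strongest case for a change is that the gap is real and cheap to close. The schedule row concerns drain content, not just volume, and no rule says whether a finding there counts as an event. Leak is plainly of interest: every patient is tested for it, and criteria g and h place drains because of doubt about the anastomosis or the duodenal stump. The contrast study is described only for anastomotic leaks, so a stump leak has no stated shared test. Examination and laboratory tests are non-specific and have no written trigger for further work-up. One definition, one field recording how an event was first detected and one extra table would need no new procedure.

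Part of this stands. No event criteria are written, and unequal detection is possible in principle. But the harm needs two things that the documents do not show: that leak or a similar event is compared, and that drain fluid was used to diagnose it. The route of first detection is not a scheduled item, and the analysis is described in the past tense, so the field may be impossible to complete. The extra table would remove events from one group only, on a feature known after the outcome, and could discard genuine leaks that the drain controlled. The protocol also relies on a departmental perioperative protocol that is not reproduced, so common work-up rules may or may not exist there.

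**Conclusion.** The observation is accurate, but it does not call for a change to the plan. What is left once the two undocumented conditions are set aside is an unwritten event definition. Analysts have to supply one to count any leak, and can supply one that a patient without a drain can also meet. Shared surveillance runs to discharge with the same marks after POD2 as drain content, which limits the gap without closing it.

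The size is unknown. It is nil if drain fluid played no part in diagnosis, and a ratio of up to 1.25 (2 points at a 10% risk) if 20% of events go unrecorded without a drain and all are revealed with one. Poorer assumed detection gives more, such as 1.58 for 60% against 95%. All of these assume equal true risk, which criteria a to h make doubtful, and neither a definition nor a sensitivity table would remove that confounding.

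An analysis without drain-detected events could be shown as exploratory if the records allow it. It should not be paired with the full count as limits on the true ratio. If leaks are reported, possible unequal detection belongs among the limitations.

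### The only schedule ends at discharge, so it leaves no time to observe readmissions after a stay to POD5 or later, and mortality is in effect an unlabelled in-hospital outcome

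*Combined protocol and SAP*

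**What the plan says.** The Study Protocol text points to a single timeline: "A descriptive timeline of the protocol is presented in the the table below". That table is Appendix 1. Its timepoints are two enrolment columns, the day of surgery, POD1 to POD5, and Ω. Footnote c) defines the last column as "Ω: time between POD#5 and discharge".

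Among the monitoring rows, "READMISSIONS" and the mortality row each carry six marks: POD1, 2, 3, 4, 5 and Ω. Other rows, such as "EXTRAABDOMINAL COMPLICATIONS" and surgical site infection, stop at POD5.

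The statistical analysis paragraph names no outcome variables. It says "Comparisons were preformed between patients with drainage and those without drainage", and that "for the qualitative parameters statistical tests were performed via the chi-square test", with Fisher's exact test where needed. It gives no time window for any outcome. Nothing elsewhere in the documents describes a visit, a call or a record check after discharge, or says whether mortality means in-hospital, 30-day or something else.

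**The concern.** Readmission is listed as something to monitor, yet the last period in which it is to be monitored closes at the moment the patient first becomes able to have one. For a patient who stays to POD5 or beyond, the mark in Ω covers no time at risk.

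The trial asks whether a prophylactic drain can be omitted. A complication that shows itself after discharge would be expected to appear as a readmission or a death. If readmissions are compared on the written schedule, the count will be zero or close to it in both groups. A reader could take that as reassurance about leaving out the drain, although the schedule could not have shown otherwise.

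For mortality the problem is milder. In-hospital death is a legitimate outcome, but the plan does not label it so, and a patient who stays longer is watched longer. Crude death frequencies are then comparable between groups only if stays and discharge practice are similar.

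**Working it through.** The documents state no follow-up length, event rate, group size or length of stay, so there is no figure of the plan's own to reproduce. The check is a reading of the schedule plus simple counting.

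**Inputs**
- Marked columns for readmissions and mortality: POD1 to POD5 and Ω (Appendix 1).
- End of Ω: discharge (footnote c).
- Expected course (Study Protocol text): soft diet is reached on POD4. In the drain group "the drain was removed on the fifth postoperative day", subject to an output condition. A stay to about POD5 is therefore the natural reading, although no discharge day is stated.

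**Step 1: readmissions.** Let *d* be the postoperative day of discharge. Suppose the POD columns still apply to someone who has already gone home, which is the generous reading. Full post-discharge days inside a marked column are then max(0, 5 − *d*):

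| Discharge day *d* | Post-discharge days covered |
|---|---|
| POD3 | 5 − 3 = 2 |
| POD4 | 5 − 4 = 1 |
| POD5 or later | 0 |

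Ω adds nothing, because it ends at discharge. A return on POD5 itself, by a patient sent home that day, is an edge case that does not change the picture.

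**Step 2: what a comparison would show.** If no readmission is recorded in either group, the two-by-two table has an event total of 0. Only one table is possible with those margins, so Fisher's p is 1.00 whatever the group sizes. The expected counts in the event column are 0, so the chi-square statistic is 0/0. This is true of any empty table and is not a prediction for this trial. It shows why such a result would carry no information about drains.

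**Step 3: mortality.** For a patient discharged alive on day *d*, deaths can be recorded on the written schedule up to day max(*d*, 5). Discharge on POD5 gives 5 days of observation from surgery; discharge on POD10 gives 10. Against a 30-day window from surgery (an assumption; the documents give none), the unobserved part is 30 − 5 = 25 days and 30 − 10 = 20 days respectively. Observation time therefore moves with length of stay. Without stays by group, neither the size nor the direction of any effect on the comparison can be worked out.

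**The case against.** The strongest reply is that the table is being read too literally. The text calls it descriptive. The length-of-stay, mortality and readmission rows have identical marks, which may be routine filling-in, and a readmission mark at POD1 makes little practical sense. Listing readmissions shows that someone meant to record them. The departmental perioperative protocol is not reproduced and the consent pages have been removed; either might describe follow-up. The reoperations row has no marks at all in the extracted table, so the table's reliability is open to question. Finally, the statistical paragraph does not name readmission as a tested variable.

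Part of this stands. The table may be incomplete, and the blank reoperations row may be an effect of reading the PDF. It is also right that no readmission test is named, so the harm in Step 2 is conditional on one being made. But none of these points supplies a window or overrides footnote c), which is explicit. The table does distinguish rows that run into Ω from rows that stop at POD5, so its last column is not meaningless. The blank row does not disturb the six marks that fill the readmissions row to its final column.

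A reader might go further and infer that deaths after discharge were excluded, or that no follow-up took place. The documents say neither; they give no time point or method for finding such events. Nor are all post-discharge deaths outside the schedule: someone discharged before POD5 is formally covered to POD5. A reader might also infer that mortality is biased in favour of one group. With no stays reported, that is not supported.

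**Conclusion.** The point holds and should be fixed. On the only schedule given, readmission is unobservable for a patient discharged on POD5 or later (0 post-discharge days) and barely observable for earlier discharges (1 day after POD4, 2 after POD3). A between-group comparison of readmissions on that basis would be uninformative. This is a consequence of a stated rule, not merely of missing detail.

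For mortality the finding is smaller: an in-hospital outcome (to POD5 for earlier discharges) that is not labelled as such, with an observation time that depends on length of stay. Its effect on the comparison is unquantified.

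The conclusion assumes that the schedule was followed as written and that no document outside those provided sets a window. The count of 0 days at POD5 or later does not depend on any choice of follow-up window.

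**What to change.** Define one fixed window per event, the same in both groups. For example: death within 30 days of surgery for all patients, and readmission within 30 days of discharge for those discharged alive. Thirty days is illustrative; what matters is that the window is fixed and common.

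The plan is written in the past tense ("The statistical analysis was performed using the R software"). If accrual is complete, retrieve the events from records or by call before analysis. If patients are still being enrolled, use one call or record check at the end of the window. Base the group comparisons on these windows and report completeness of ascertainment per group. Correct footnote c) and the two rows to match, and check the blank reoperations row at the same time.

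If the data cannot be retrieved, label mortality as in-hospital and make no group comparison of readmissions.

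The cost is one call or record check per patient, a change of wording, later data closure and possibly an IRB amendment. Some patients will be lost to follow-up, and a records search may miss events treated at other hospitals. The change does not deal with confounding from placing drains on risk criteria, nor with late complications that lead to neither death nor readmission.
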